14.1.1.1.2. Secondary Efficacy Endpoint

The secondary efficacy endpoint is:

Survival at 14 months of age amongst symptomatic SMA Type 1 patients who are homozygous negative for *SMN1* exon 7 and have 2 copies of *SMN2* without the *SMN2* genetic modifier.

Survival is defined by the avoidance of the combined endpoint of either (a) death or (b) permanent ventilation, which is defined by tracheostomy or by the requirement of ≥ 16 hours of respiratory assistance per day (via non-invasive ventilator support) for ≥ 14 consecutive days in the absence of an acute reversible illness, excluding perioperative ventilation. Permanent ventilation, so defined, is considered a surrogate for death.

- An “acute reversible illness” is defined as any condition other than SMA that results in increased medical intervention (i.e., increased requirement for respiratory support; use of other concomitant medications as rescue) requirements and is expected to be reversible or improved following definitive intervention (i.e., surgery, antibiotics) or introduction of escalated supportive care, such as hospitalization (i.e., for upper respiratory infection, spontaneous fracture). The specific duration of the condition antecedent intervention

shall not be considered in the definition of “acute.” The date of “definitive intervention” shall be defined as the date of provision of a procedure (i.e., surgery, etc.) or medication (i.e., antibiotics) intended to cure or substantially improve the condition. For conditions such as viral respiratory infections for which supportive care is provided, the date of “definitive intervention” shall be considered the date of hospitalization or substantial escalation of care.

- “Perioperative” use reflects any alteration of ventilator use related to a surgical or other medical procedure of any nature for which the patient received medications that could impair or interfere with respiratory function.
- For a patient who develops an acute reversible illness and/or requires perioperative ventilator support, a recovery period not to exceed 21 days following the date of definitive intervention will be instituted. Following this recovery period, the condition will be considered subacute and the patient will become evaluable with regards to the surrogate survival endpoint (requirement of ventilator support of ≥ 16 hours/day for 14 or more days).

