1.2. Glossary of Definitions

Abbreviations list pertains to the SAP only.

| Abbreviation | Description |
|-----------------|--|
| AE | Adverse Event: Any untoward medical occurrence in a clinical investigation subject which does not necessarily have a causal relationship with the drug or device under study. |
| Age | For a given event, age will be expressed in months and rounded to one decimal place. A month is standardized to a period of 30 days. Age at Event = (Date of Event – Date of Birth + 1)/ 30. Age at Dosing = (Date of Gene Therapy Infusion – Date of Birth + 1)/ 30. |
| Baseline | Baseline, e.g., in terms of baseline laboratory values, vital signs, or physical exam results, refers to a measurement or evaluation made prior to initiation of gene therapy infusion. If there are multiple measurements prior to the initiation of gene therapy infusion, only the latest measurement will be considered as baseline for analysis purposes. |
| BiPAP | Bilevel Positive Airway Pressure, a form of non-invasive mechanical pressure support ventilation. |

| Abbreviation | Description |
|------------------------------|---|
| CHOP-INTEND | Children’s Hospital of Philadelphia Infant Test of Neuromuscular Disorders, a 16-item motor function assessment validated for use in infants with spinal muscular atrophy. |
| Day 1 | The day of the gene therapy treatment. |
| Dose | Total vector genome administrated (in vg /patient weight on Day – 1(kg)). |
| MedDRA | Medical Dictionary for Regulatory Activities is a medical terminology used to classify adverse event information associated with the use of biopharmaceuticals and other medical products. |
| CTCAE | Common Terminology Criteria for Adverse Events version 4.03. The CTCAE is descriptive terminology, involving a severity scale, which is used for AE reporting in particular for unique patient populations. It is a subset of MedDRA terminology. |
| Permanent Ventilation | Requirement of ≥ 16 -hour respiratory assistance per day (includes BiPAP) continuously for ≥ 14 days in the absence of an acute reversible illness, excluding perioperative ventilation. |
| PNCR | Pediatric Neuromuscular Clinical Research Network |
| Study Day | For any event of interest, Study Day = calendar date of event – calendar date of gene transfer +1. Day 1 is the Study Day of the gene transfer and any events occurring on the same calendar day as the gene transfer. |

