4.1.2. Secondary Efficacy Endpoints

The secondary efficacy endpoint is survival, defined as avoidance of either (a) death or (b) permanent ventilation through the 14 month of age visit. Permanent ventilation is defined by tracheostomy or requirement of ≥ 16 hours of respiratory assistance per day (via non-invasive ventilatory support) for ≥ 14 consecutive days in the absence of an acute reversible illness, excluding perioperative ventilation. Permanent ventilation, so defined, is considered a surrogate for death.

The respiratory assistance includes but is not limited to BiPAP machines, for example, Philips Trilogy 100 machine. Particularly, Trilogy 100 usage data will be saved in the SD card when patient uses the machine. Data in the SD card will be sent to AveXis by site during clinical visit. Daily usage information will be available when using DirectView software to extract the “compliance summary” from the raw data (.EDF files).

In addition, each site will be asked to verify whether permanent ventilation criteria were met for each patient. If a patient is reported to necessitate permanent ventilation, the date at which permanent ventilation was met will be reported by site.

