5.6. PNCR Control Population

The PNCR Natural History dataset is drawn from a large natural history study ([Finkel, 2014](#)) performed on a large cohort of 337 patients with any form of spinal muscular atrophy followed at 3 large, internationally recognized tertiary medical centers with significant expertise in the management of SMA (Harvard University/Boston Children's Hospital, Columbia University and the University of Pennsylvania/Children's Hospital of Philadelphia). Previously identified patients followed in PNCR site clinics and newly diagnosed patients were enrolled. All eligible patients were offered participation in the PNCR study. Study visits were scheduled at baseline and at 2, 4, 6, 9, and 12 months and every 6 months thereafter. The SMA standard of care

guidelines ([Wang, 2007](#)) were used as a basis for providing uniform care among the study sites. For purposes of this study, sitting (for SMA Type 2) was defined as being able to sit independently for >10 seconds; children who were unable at any point to achieve this milestone were classified as SMA Type 1.

A natural history control population is drawn from the PNCr Natural History Dataset ([Finkel, 2014](#)) consisting of all patients with age of onset ≤ 6 months, bi-allelic deletion of *SMN1* (exon 7/8 common homozygous deletion) and 2 copies of *SMN2* for whom enrollment data (retrospective and prospective) is available to determine survival based on the defined criteria. The *SMN2* modifier mutation (c.859G>C) described by Prior and colleagues (Prior, Thomas W., et. al. "A positive modifier of spinal muscular atrophy in the *SMN2* gene." *The American Journal of Human Genetics* 85.3 (2009): 408-413.) was not assessed in the PNCr study cohort. Based on these criteria, 23 patients from the PNCr dataset are included in the control population. Among them, 16 patients reached the combined endpoint of death or the need for a minimum of 16 hours/day of noninvasive ventilation support for a minimum of 14 continuous days by 14 month of age and one patient discontinued the study at age of month 4. The survival rate at 14 months of age is approximately 25% (6/23), of which the control cohort will be used as comparator with ITT population for survival analysis.

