6.2.4.2. Supportive (Secondary and exploratory) Efficacy Variables

The secondary efficacy endpoint, event-free survival, is defined as avoidance of any one of the following events up to 14 months of age, whichever occurred first:

- Death, *or*
- Tracheostomy, *or*
- Noninvasive Ventilatory support ≥ 16 -hour per day *and* continuously ≥ 14 days

Usage data for patients using non-invasive ventilatory support will be extracted directly from the device (e.g., Trilogy 100, Trilogy 200, ResMed Stellar) on an SD card, or USB stick and transferred as an external dataset, if available. Average daily use of non-invasive ventilatory support at baseline and monthly be summarized from data recorded on an SD card or USB stick and submitted in a format that is evaluable. If a patient did not have a device with the capability to record usage data at baseline and was using non-invasive ventilatory support prior to screening, the daily usage will be documented in the source documentation. As a secondary analysis, the amount of ventilation support will be categorized into None, $>0-\leq 12$ hours, $>12-\leq 16$ hours, ≥ 16 or permanent ventilation. At each of the above time points, the count and percent of patients in each ventilation support category will be presented.

Supportive (exploratory) efficacy variables are as follows:

- CHOP-INTEND summary score: This is assessed by evaluating the Baseline CHOP-INTEND scores compared to each scheduled visit time points (see [Table 4](#)), collected from patient's CRF. A summary score is obtained by summing the individual best-side scores.
- Achievement of Selected Threshold Scores on CHOP-INTEND: clinically relevant threshold scores were determined for categorizing CHOP-INTEND summary scores: ≥ 40 , ≥ 50 , ≥ 58 .
- Bayley Scales of Infant and Toddler Development[®] version 3: Two domains of motor and adaptive behavior will be assessed from patient's CRF at scheduled visits (see [Table 1](#)) with both raw and scaled scores provided.
- Age at which independent sitting (for 10 seconds) is first achieved.
- Ability to remain independent of ventilator support, defined as requiring no daily ventilator support/usage at 18 months of age.
- Ability to thrive as defined by maintaining the ability to swallow and to maintain weight ($>$ third percentile based on WHO CGRS without need of gastrostomy or other mechanical or non-oral nutritional support at 18 months of age)

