8.2. Secondary Efficacy Endpoints and Analysis

8.2.1. Secondary Efficacy Endpoint: Avoidance of Death or Surrogate for Death (Permanent Ventilation)

The secondary efficacy endpoint is defined by avoidance of the combined endpoint of either (a) death or (b) permanent ventilation, defined as requirement of tracheostomy or ≥ 16 hours of respiratory assistance per day (includes non-invasive ventilatory support) continuously for ≥ 14 days in the absence of an acute reversible illness, excluding perioperative ventilation. Permanent ventilation, so defined, is considered a surrogate for death.

Non-invasive ventilatory support usage data (only available from Trilogy 100) will be extracted directly from each patient's device; the data will be downloaded from the device's SD card through software provided by the manufacturer and transferred as an external dataset.

An "acute reversible illness" is defined as any condition other than spinal muscular atrophy that results in increased medical intervention (i.e., increased requirement for external ventilator support; use of other concomitant meds as rescue) requirements and is expected to be reversible or improved following definitive intervention (i.e., surgery, antibiotics) or introduction of escalated supportive care, such as hospitalization (i.e., for upper respiratory infection, spontaneous fracture). The specific duration of the condition antecedent intervention shall not be considered in the definition of "acute". The date of "definitive intervention" shall be defined as the date of provision of a procedure (i.e., surgery, etc.) or medication (i.e., antibiotics) intended to cure or substantially improve the condition. For conditions, such as viral respiratory infections, for which supportive care is provided, the date of "definitive intervention" shall be considered the date of hospitalization or substantial escalation of care.

"Perioperative" use reflects any alteration of ventilator use related to a surgical or other medical procedure of any nature for which the participant received medications that could impair or interfere with respiratory function.

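### The SAP's event rules for the secondary survival endpoint conflict: prolonged endotracheal ventilation without tracheostomy is event-free under the derived variable and an event under the analysis section

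*SAP*

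**What the plan says.** Event-free survival at 14 months of age is the only secondary endpoint. It is tested after the primary endpoint in a fixed order (SAP 3.11.2 and 8.4), by two-sided Fisher's exact test against 23 PNCR natural history controls. An event is death or permanent ventilation, and permanent ventilation is described in several ways.

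- **Non-invasive only, apart from tracheostomy.** Protocol 14.1.1.1.2: "respiratory assistance per day (via non-invasive ventilator support". SAP 4.1.2: "respiratory assistance per day (via non-invasive ventilatory support", with the same limit in SAP 3.2. The derived variable in SAP 6.2.4.2 lists death, tracheostomy and "Noninvasive Ventilatory support ≥ 16 -hour per day".
- **Not limited to non-invasive.** SAP 8.2.1, the analysis section: "respiratory assistance per day (includes non-invasive ventilatory support) continuously". The glossary in SAP 1.2: "respiratory assistance per day (includes BiPAP) continuously". The recovery-period text in Protocol 14.1.1.1.2 and SAP 8.2.1 speaks only of ventilator support.
- **Controls.** SAP 5.6 describes PNCR events as death or "noninvasive ventilation support for a minimum of 14 continuous days by 14 month of age".

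No section mentions endotracheal ventilation or states which wording governs.

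**The concern.** Permanent ventilation is there to stand in for death. *Via* confines the criterion to non-invasive support; *includes* does not. The two rules differ for an infant who stays on an endotracheal tube well past the recovery period without receiving a tracheostomy, which is about as severe as respiratory failure gets short of death. One rule in the SAP calls that infant a survivor and another calls the infant an event.

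The trial is open-label and single-arm. If such an infant exists, the outcome is known before anyone must decide which section to program. That leaves room for choice in an endpoint carrying a confirmatory test, and it bears directly on the survival percentage that will be reported.

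**Working it through.** **1. The plan's own figure.** Inputs: 25 treated infants, 80% v 25% survival, two-sided Fisher's exact test, alpha 0.05 (Protocol 14.2, SAP 3.7); 23 controls (SAP 5.6). Power is the sum over x and y of Bin(x; 25, 0.80) × Bin(y; 23, 0.25), taken over outcomes with p ≤ 0.05 favouring treatment. Result: 97.6%, or 97.9% if 25 controls are assumed. The stated bounds (over 90% in Protocol 14.2 and SAP 3.7; at least 95% in the Protocol Synopsis) are met. The power claim is not in dispute.

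**2. The definitions side by side.**

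| Place | Modes in the 16-hour criterion | Tracheostomy named | Acute-illness and perioperative exemptions | Duration |
|---|---|---|---|---|
| Protocol 14.1.1.1.2 | non-invasive; recovery text says any ventilator support | yes | yes | 14 days or more |
| SAP 1.2 | assistance including BiPAP | no | yes | 14 days or more |
| SAP 3.2, 4.1.2 | non-invasive | yes | yes | 14 days or more |
| SAP 6.2.4.2 | non-invasive | yes | no | 14 days or more |
| SAP 8.2.1 | assistance including non-invasive; recovery text says any ventilator support | yes | yes | 14 days or more in the definition; more than 14 in the recovery text |

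The worked example in 8.2.1 runs from day 22 to day 36, which is 36 − 22 + 1 = 15 days. It follows the stricter duration; a rule of 14 days or more would be met on day 35.

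**3. A test case.** An infant is intubated for at least 16 h/day, for at least 15 days after the 21-day recovery period (long enough under either duration rule), and has no tracheostomy. Under 6.2.4.2 none of the three listed events has occurred, so the infant is event-free. Under 8.2.1 the infant has received the required respiratory assistance and is an event.

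**4. Size.** Each reclassified infant moves treated survival by 1/25 = 4 percentage points. The planned 80% is 20/25. The documents give no count of such infants; the rows below are an assumed illustration, with controls held at 6/23 (26.1%).

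| Reclassified | Treated survival | Fisher two-sided p v 6/23 |
|---|---|---|
| 0 | 20/25 = 80% | 0.0004 |
| 1 | 19/25 = 76% | 0.0012 |
| 2 | 18/25 = 72% | 0.0034 |
| 3 | 17/25 = 68% | 0.0047 |
| 6 | 14/25 = 56% | 0.045 |
| 7 | 13/25 = 52% | 0.083 |

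Significance needs at least 14/25, so it is lost at 20 − 13 = 7 reclassified infants.

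The same shift can be read as a lower true rate at the design stage. With the formula in step 1 and controls still at 25%, power is 97.6% at a true rate of 80%, 95.0% at 76%, 91.0% at 72% and 85.4% at 68%. With controls fixed at 6/23, the chance of reaching 14/25 is 99.8% at 80% and 93.0% at 68%.

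**The case against.** The strongest reply is that the SAP already points to one definition. The heading of 4.1 refers the reader to Section 8 for details. Section 8.2.1 carries the definition, the exemptions, an example and the statistical approach, and its wording is the broader one. SAP Section 2 says the SAP supersedes the protocol's statistical considerations. In addition, SAP 4.1.2 has each site verify whether the criteria were met, and 4.6.10 has the investigator assess every patient, so an infant intubated for weeks would not pass unnoticed. SAP 4.1.2 also adds that assistance is not confined to BiPAP machines.

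Most of this stands, and it lowers the risk. It does not remove it. Section 6.2.4.2 is where the variable is derived, and it states a different rule within the same SAP. Sites work from a protocol whose definition says "via non-invasive ventilator support". The instruction to record ventilator usage in the eCRF (Protocol 12.1.7) names only non-invasive support, and the SAP's device data come from non-invasive machines. The remark about BiPAP may mean no more than other non-invasive devices.

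The case is also narrow. Where acute illness or surgery is involved, up to 21 days are exempt and about 14 more are required, so roughly five weeks of intubation with neither death nor tracheostomy.

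Finally, the non-invasive wording matches how the PNCR events are described, so broadening the rule for treated infants alone would create a new mismatch. That is a sound objection to a one-sided change, and the fix has to cover both cohorts.

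**Conclusion.** The SAP holds conflicting event rules for its sole secondary endpoint, and they classify at least one describable infant in opposite ways. Three smaller conflicts accompany this: 6.2.4.2 drops the acute-illness and perioperative exemptions, the glossary drops tracheostomy, and 8.2.1 uses both at least 14 and more than 14 days.

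Three stronger readings are tempting and are not supported.

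- A reader might infer that long-intubated infants will be counted as survivors. The pointer to Section 8 and the site verification make this possible, not certain.
- A reader might infer that the significance of the survival test is at stake. At the planned 20/25 it would take seven reclassified infants, and even three leave p = 0.0047. Extending the rule to the controls could only leave or lower their six survivors, which would partly offset the shift.
- A reader might infer that infants with a tracheostomy could be missed. Only the glossary omits tracheostomy; the derived variable and the analysis section both name it.

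The effect is therefore mainly on the reported survival rate, at 4 points per infant, and on whether the rule was fixed before the outcomes were known. This rests on 25 treated infants, the planned 80% and the stated 6/23. The number of affected infants is not given and is probably small.

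**What to change.** Before database lock, reconcile the passages to one analysis definition by aligning SAP 1.2, 3.2, 4.1.2 and 6.2.4.2 with the SAP's own 8.2.1: tracheostomy, or at least 16 h/day of respiratory assistance, including but not limited to non-invasive support, on at least 14 consecutive days, with the existing exemptions. Make the recovery-period sentence and the day-36 example in 8.2.1 agree with that duration. Record the departure from the wording of Protocol 14.1.1.1.2 in SAP Section 13, as SAP Section 2 requires for substantial differences.

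Identify any invasive-ventilation days from hospitalisation records already held; in-patient hospitalisation is itself a serious adverse event criterion (Protocol 13.1.2), so the stays should be traceable.

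Apply the same rule to the PNCR records where ventilation mode was recorded. Where it was not, say so and report the non-invasive-only version as a sensitivity analysis, so that the two cohorts are also compared on the same events.

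The cost is SAP wording, a short check of hospital records and a check of what PNCR recorded. Treated survival may come out slightly less favourable.

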4.2. Exploratory Efficacy Endpoints: (see [Section 8](#) for Details)

For the following exploratory efficacy endpoints from achieving the ability to hold head erect to the ability to walk alone, only post-dosing achieved developmental milestones are considered. Milestones observed at baseline will not be counted in the summary table.

1. Proportion of patients that achieve the ability to hold head erect without support as defined by BSIDv03 Gross Motor Subtest Item #4
2. Proportion of patients that achieve the ability to roll over as defined by BSIDv03 Gross Motor Subtest Item #20
3. Proportion of patients that achieve functional independent sitting for at least 30 seconds as defined by BSIDv03 Gross Motor Subtest Item #26
4. Proportion of patients that achieve ability to stand with assistance for at least 2 seconds as defined by BSIDv03 Gross Motor Subtest Item #33

5. Proportion of patients that achieve to crawl forwards on hands and knees for a distance of at least 5 feet as defined by BSIDv03 Gross Motor Subtest Item #34
6. Proportion of patients that achieve to walk with assistance as defined by BSIDv03 Gross Motor Subtest Item #37
7. Proportion of patients that achieve to stand alone for at least 3 seconds as defined by BSIDv03 Gross Motor Subtest Item #40
8. Proportion of patients that achieve to walk at least 3 steps without support as defined by BSIDv03 Gross Motor Subtest Item #42
9. Proportion of patients that achieve the ability to crawl as defined by WHO Motor Developmental Milestones
10. Proportion of patients that achieve the ability to stand with assistance as defined by WHO development milestones
11. Proportion of patients that achieve the ability to stand alone as defined by WHO development milestones
12. Proportion of patients that achieve the ability to walk with assistance as defined by WHO development milestones
13. Proportion of patients that achieve the ability to walk alone as defined by WHO development milestones
- Improvement of raw score from baseline to the maximum using the Bayley Scales of Infant and Toddler Development (Version 3)
14. , Fine and Gross Motor Function Subtests
15. Maximum change from baseline to maximum CHOP-INTEND score
 - Proportion of patients achieving CHOP-INTEND score ≥ 40
 - Proportion of patients achieving CHOP-INTEND score ≥ 50
 - Proportion of patients achieving CHOP-INTEND score ≥ 58
16. Proportion of patients with the ability to remain independent of ventilator support, defined as requiring no daily ventilator support/usage at 18 months of age.
17. Proportion of patients maintaining the ability to thrive.
18. Age at which patient first achieves independent sitting (10 seconds).

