5.4. Efficacy Completers Population

The efficacy completers analysis population will consist of:

- All treated patients who reach 14 months of age for the survival endpoint or 18 months of age for the endpoint of achievement of sitting without support, OR
- All treated patients who meet discontinuation criteria, discontinue the study due to an AE, or experience death

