8.3. Exploratory Efficacy Endpoint(s) and Analyses

The exploratory efficacy analyses will be based on Efficacy Completers Population. Due to COVID-19 impact, any efficacy data collected outside of the SAP-defined visit window of Month 18 of age visit (older than 570 days of age) will be grouped into “Month 19 of age or older” and included for summary tables unless specified. The hypothesis testing will be based on the data collected up to 18 months of age. Those data will also be included in the corresponding listing.

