8.3.1. Proportion of Patients that Achieve Ability to Hold Head Erect Without Support

The ability to hold head erect without support is defined by BSIDv03 Gross Motor Subtest Item #4 and will be based upon the maximum function achieved at any time point up to 18 months of age.

The numbers and percentages of patients who achieve the ability to hold head erect without support by the final visit will be presented by overall, including subgroups, age at the time of treatment (≤ 4 months, > 4 months). The observed proportion achieving the ability to hold head erect without support during the observation period will be compared to zero using a 1-sided Exact Binomial Test, along with the corresponding 97.5% confidence intervals. To make computation of the p-value possible, the value of 0.1% will be used in place of a literal zero.

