8.3.17. Achievement of Selected Threshold Scores on CHOP-INTEND

8.3.17.1. Proportion of Patients Achieving CHOP-INTEND Score ≥ 40

The numbers and percentages of patients who achieve CHOP-INTEND score ≥ 40 by the final visit will be presented by overall and by subgroups, including subgroups, age at the time of treatment (≤ 4 months, > 4 months). The observed proportion achieving CHOP-INTEND score ≥ 40 during the observation period will be compared to zero using a 1-sided Exact Binomial Test, along with the corresponding 97.5% confidence intervals. To make computation of the p-value possible, the value of 0.1% will be used in place of a literal zero. Patients with baseline scores ≥ 40 will not be considered in the proportional analysis.

8.3.17.2. Proportion of Patients Achieving CHOP-INTEND Score ≥ 50

The numbers and percentages of patients who achieve CHOPINTEND score ≥ 50 by the final visit will be presented by overall and by subgroups, including subgroups, age at the time of treatment (≤ 4 months, > 4 months). The observed proportion achieving CHOP-INTEND score ≥ 50 during the observation period will be compared to zero using a 1-sided Exact Binomial Test, along with the corresponding 97.5% confidence intervals. To make computation of the p-

value possible, the value of 0.1% will be used in place of a literal zero. Patients with baseline scores ≥ 50 will not be considered in the proportional analysis.

8.3.17.3. Proportion of Patients Achieving CHOP-INTEND Score ≥ 58

The numbers and percentages of patients who achieve CHOP-INTEND score ≥ 58 by the final visit will be presented by overall and by subgroups, including subgroups, age at the time of treatment (≤ 4 months, >4 months). The observed proportion achieving CHOP-INTEND score ≥ 58 during the observation period will be compared to zero using a 1-sided Exact Binomial Test, along with the corresponding 97.5% confidence intervals. To make computation of the p-value possible, the value of 0.1% will be used in place of a literal zero. Patients with baseline scores ≥ 58 will not be considered in the proportional analysis.

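### SAP 4.2 does not count milestones already present at baseline, but 8.3 has no rule taking those infants out of the denominator; on the default reading, exploratory milestone proportions come out too low

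*SAP*

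**What the plan says.** - **What counts as an achievement.** SAP 4.2, for the milestones from head control to walking alone, says "only post-dosing achieved developmental milestones are considered" and adds "Milestones observed at baseline will not be counted in the summary table". It names no denominator.
- **Who is analysed.** SAP 8.3: "The exploratory efficacy analyses will be based on Efficacy Completers Population". SAP 5.4 defines that set as treated patients who reach the relevant age, or who meet discontinuation criteria, stop because of an adverse event, or die. Baseline motor status plays no part.
- **How each milestone is reported.** SAP 8.3.1 presents "The numbers and percentages of patients who achieve the ability to hold head erect without support by the final visit", and its definition of the milestone "will be based upon the maximum function achieved at any time point up to 18 months of age". Sections 8.3.2 to 8.3.14 follow the same pattern. None repeats the 4.2 exclusion or removes baseline achievers.
- **The contrasting rule.** In 8.3.17.1 to 8.3.17.3, patients already at the CHOP-INTEND threshold at baseline "will not be considered in the proportional analysis".
- **The protocol.** Section 14.1.1.1.3 calls a patient a responder if the endpoint is shown at any visit after dosing, up to the 18-month visit. It makes no exception for a skill held at baseline.

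**The concern.** Put together, SAP 4.2, 5.4 and 8.3 place an infant with a baseline skill in the denominator and bar that infant from the numerator. The infant is reported as not achieving something the baseline video shows and which may never have been lost. The same SAP handles the identical situation differently for CHOP-INTEND, with the same exact test against 0.1%.

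Such infants are foreseeable. Protocol 11.2.2 requires a video-recorded baseline milestone assessment at screening, and SAP 3.6 allows pre-symptomatic infants, who are outside the ITT population but can be completers.

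What is at stake is the descriptive value of the exploratory milestone table: the percentages, the exact intervals, and the display by age at dosing (up to 4 months, over 4 months) if baseline skills differ by age. There is also a reproducibility problem, because two programmers could derive different proportions from the current text.

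**Working it through.** **1. The plan's own figure.** The documents give no expected value for the exploratory milestones. The nearest figure is the power of the same test for the primary endpoint (SAP 3.7): n = 25, null 0.1%, one-sided 0.025, true rate 20% to 50%, power above 95%. Rejecting with at least one responder gives:

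- alpha = 1 - 0.999^25 = 0.0247
- power at 20% = 1 - 0.8^25 = 0.996; at 50% it exceeds 0.9999

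The stated figure reproduces. The 4.2 rule does not apply to the primary endpoint, so this power is unaffected.

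**2. Inputs for the milestones.**

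- N = 30 completers: an assumption, taken from the planned enrolment in SAP 3.7.
- b = completers with the milestone at baseline: not in the documents, so varied from 0 to 10.
- x = completers who newly achieve it after dosing: an assumption, set at 80% of the N - b infants who could, rounded.

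**3. The three proportions the current text could yield.**

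- A, baseline achievers kept in the denominator (default reading): x/N
- B, baseline achievers removed (the 8.3.17 rule): x/(N - b)
- C, protocol responder, if all b show the skill again after dosing: (x + b)/N

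A/B = (N - b)/N, whatever x is.

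| b | x | A = x/30 | B = x/(30 - b) | C = (x + b)/30 | A/B |
|---|---|---|---|---|---|
| 0 | 24 | 80.0% | 80.0% | 80.0% | 1.000 |
| 1 | 23 | 76.7% | 79.3% | 80.0% | 0.967 |
| 3 | 22 | 73.3% | 81.5% | 83.3% | 0.900 |
| 5 | 20 | 66.7% | 80.0% | 83.3% | 0.833 |
| 10 | 16 | 53.3% | 80.0% | 86.7% | 0.667 |

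**4. Intervals.** The exact (Clopper-Pearson) two-sided 95% limits are beta quantiles: 0.025 of Beta(x, n - x + 1) and 0.975 of Beta(x + 1, n - x). For b = 3, 22/30 gives 54.1% to 87.7% and 22/27 gives 61.9% to 93.7%. The whole interval moves down, though its limits do not scale by exactly 0.90.

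**5. Tests against 0.1%.** With 10 or more new achievers, p is below 1e-22 on either denominator. The decision can differ only with a single new achiever: p = 1 - 0.999^30 = 0.0296 at n = 30 (not significant) against 0.0247 at n = 25 (significant). One responder suffices up to n = 25; two are needed from 26 to at least 33. At N = 30 this requires b of at least 5 together with x = 1.

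**The case against.** The strongest reply is that a reader might infer that the SAP instructs keeping baseline achievers in the denominator, and it does not. No sentence says so. Not counting a baseline milestone in the table could also mean dropping that infant for that milestone, as for CHOP-INTEND. This stands. What can be said is that the denominator is unstated and that 8.3 with 5.4 makes retention the default.

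Second, the numerator is not settled either. SAP 4.2 refers to Section 8 for details, where function at any time point is used, and the protocol counts any visit after dosing. Protocol 11.1 also has all milestones reassessed at 18 months whatever was attained before. If those texts govern, an infant who keeps the skill counts and nothing is understated. This also stands, and it shows that SAP 4.2 conflicts with SAP 8.3 and with the protocol. SAP Section 2 promises to identify substantial departures from the protocol; Section 13 lists only the completers definition.

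Third, new acquisitions over all completers is a coherent, conservative quantity, and any error runs against the product. That is true, but neither the table description nor the endpoint wording says that this is the quantity meant.

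Fourth, the reach is narrow. Protocol 5.2 says Type 1 patients never sit independently, and 14.2 expects no rolling, standing or walking without treatment in the ITT-type population. Head control is therefore the main candidate, plus whatever pre-symptomatic infants can already do. The age groups are only displayed for milestones, not formally compared. Both limits are accepted.

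**Conclusion.** The point holds as a low-severity issue of analysis definition. SAP 4.2 states an exclusion without its denominator, and the default reading gives a proportion too low by the factor (N - b)/N, relative to infants who could newly achieve the milestone. At an assumed N of 30, the loss is about 3% of the value for b = 1, 10% for b = 3 and 17% for b = 5. These are illustrations, since b is unknown and may be zero for most milestones.

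The documents do not support inferring that any efficacy claim is put at risk. The endpoints are exploratory, the tests against 0.1% are practically unchanged, and the primary and secondary endpoints are outside the 4.2 rule.

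**What to change.** 1. In SAP 4.2 and 8.3.1 to 8.3.14, define the denominator for each milestone as completers without that milestone on baseline video, matching 8.3.17, and say whether the site evaluator or the central reviewer decides baseline status.
2. Report, for each milestone and age group, the number who had it at baseline.
3. Show the protocol 14.1.1.1.3 responder proportion, over all completers, as a supplement.
4. List the departure from the protocol's responder definition in SAP Section 13.
5. While editing, add pull to stand (item #35) to the 4.2 list; it is analysed in 8.3.6 but missing there.

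The cost is SAP wording and slightly smaller denominators that differ between milestones. The baseline videos are already required. The supplement may need some extra central reading: protocol 11.1 has every milestone recorded at 18 months, but for that visit 11.3 specifically names only the two sitting milestones and newly attained ones for central review. The alternative is to label those results as site-assessed.
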